5.1.4. Visit Windows

Referring to CTP Section 1.3 per protocol visit windows will be taken into account for the analysis, where applicable.

For immunogenicity-related data analysis, the PPI derivation (see details in [Section 6.3](#)) will be based on the rules which follows:

- Samples obtained after a second vaccination administered outside the time window of the planned day +/- 8 days will be excluded; as well as after a booster vaccination administered outside the time window of the planned day -30 days to +180 days (Groups 1-3).
- Samples obtained outside the following pre-defined time windows will also be excluded:
 - Pre-vaccination for sampling planned on vaccination day
 - Sampling planned day after last vaccination +/- 2 days, if the planned day is 7 days after last vaccination (e.g Day 8 post booster vaccination if given per CTP amendment 3)

- Sampling planned day after last vaccination +8 / -4 days, if the planned day is 14 days after last primary regimen vaccination (i.e. 14 days after dose 2)
- Sampling planned day after last vaccination +/- 8 days, if the planned day is 28 days or 56 days after last primary regimen vaccination (i.e. Day 29 and Day 57 post-dose 1)
- Sampling planned day between 10 and 36 days after booster vaccination, if the planned day is 14 or 28 days after booster vaccination (i.e. sampling post booster vaccination, as given per CTP amendment 3 or amendment 4)
- Sampling planned day after last vaccination +/- 30 days, if the planned day >3 months after last vaccination.

Time windows may be redefined prior to unblinding if the number of samples excluded as per the definitions above are too numerous. No time windows apply for Early Exit visit sampling.

The sample closest to the target day (at noon) will be selected, if two or more samples meet the PPI definition in the pre-defined time windows.

If some participants have undergone sampling at different timepoints than those required per CTP amendment 4 because they followed a different CTP amendment version, data from those different timepoints may be presented separately or pooled together with the most appropriate timepoint per CTP amendment 4 (e.g. all samples planned at 14 or 28 days after booster vaccination will be reported together).

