6.3. Appendix 3 The Per Protocol Immunogenicity population

The Per Protocol Immunogenicity population will include all randomized and vaccinated participants for whom immunogenicity data are available excluding participants with major protocol deviations expected to impact the immunogenicity outcomes and occurring on Day 1 or before.

In addition, samples obtained from participants will be excluded from the analysis set:

- a- after major protocol deviations expected to impact the immunogenicity outcomes and occurring after Day 1,
- b- after missed vaccinations,
- c- on or after natural SARS-CoV-2 infection (if confirmed by molecular testing or non-S-ELISA [or equivalent assay]) occurring during the study after randomization (if applicable),
- d- after other SARS-CoV-2 vaccination outside the study, or
- e- outside pre-defined time windows (Section 5.1.4).

In terms of derivation, the samples to consider for analysis on Per Protocol Immunogenicity must meet the following criteria:

Subject level

- **Crit1:** Must be randomized
- **Crit2:** Must be in FAS

- **Crit7:** No major protocol deviations with impact on immunogenicity on or before day 1 excluding Deviation Categories '85 for sample not in window', '87 for sample not stored properly'

Subject data level

Subject data to be excluded on and after the date of any of the following events:

- **Crit11:** seropositive post-Baseline by N-ELISA (value>LLOQ), if seronegative at baseline (as defined in Section [5.8.4](#))
- **Crit13:** SARS-CoV-2 infection occurring on or after Day 1
- **Crit20:** Major protocol deviations with impact on immunogenicity after day 1 except for deviation categories '85' or '87', which includes
 - **Crit21:** post SARS-CoV-2 viral vaccination outside the study occurring after Day 1
 - **Crit22:** Vacc 2 not in D57 +/- 8 days
 - **Crit23:** no Vacc 2, then exclude samples where the sample date>Day57+8.
 - **Crit24:** Vacc 3 not in D184 +180/-30 days post vacc1 – Groups 1, 2, 3
 - **Crit25:** no Vacc 3 (within 180 days post Day 184), then exclude samples where the sample date>Day184+30 – Groups 1, 2, 3

Vacc 2 refers to the 2nd dose of the primary regimen

Vacc 3 refers to booster

Sample level

Samples to be excluded on the date of deviation for '85' or '87' events:

- Crit30: major protocol deviations with impact on immunogenicity deviation categories '85' or '87', that is
 - **Crit31:** D1 sample not in window
 - **Crit32:** D29 sample not in window

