 - **Crit33:** Day 57 sample not in window
 - **Crit41:** D1 sample not stored properly (i.e. protocol deviation '87')
 - **Crit42:** D29 sample not stored properly
 - **Crit43:** Day 57 sample not stored properly

Reference to Vacc 2

- **Crit34:** Day 71 sample compared to date of Vacc2 not in window
- **Crit35:** Day 184 sample compared to date of Vacc1 not in window - Groups 1, 2, 3-
- or Day 184 sample compared to date of Vacc2 not in window - Groups 4, 5, 6-
- **Crit44:** Day 71 sample not stored properly
- **Crit45:** Day 184 sample not stored properly

Reference to Vacc 3=booster

- **Crit36:** D7 or D14 sample post Vacc3 not in window - Groups 1, 2, 3-
- **Crit37:** D184 sample post Vacc3 not in window - Groups 1, 2, 3-
- **Crit46:** D7 or D14 sample post Vacc3 sample not stored properly - Groups 1, 2, 3-
- **Crit47:** D184 sample post Vacc3 sample not stored properly - Groups 1, 2, 3-

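### In Groups 1–3 the date of a saline second injection can remove Day 184 and booster samples from the PPI, and late boosters keep their titres but lose their pre-dose-3 reference

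*SAP*

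**What the plan says.** **Second-vaccination rules.** SAP 5.1.4: "Samples obtained after a second vaccination administered outside the time window of the planned day +/- 8 days will be excluded". SAP 6.3 turns this into Crit22, "Vacc 2 not in D57 +/- 8 days", and adds Crit23 for a missed dose: "no Vacc 2, then exclude samples where the sample date>Day57+8". Both stand in the subject-data block introduced by "Subject data to be excluded on and after the date of any of the following events", with no end date and no restart at the booster. Neither carries a group label. The booster clause of the same 5.1.4 bullet does, as do Crit24, Crit25 and Crit35 to Crit37.

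**Timing in Groups 1–3.** The second injection is placebo (SAP 1.2), supplied as 0.9% NaCl (protocol 6.1). Protocol 4.1 counts the booster from Vaccination 1, the last active dose. The SAP does the same in Crit24, "Vacc 3 not in D184 +180/-30 days post vacc1", and in Crit35 for these groups, "Day 184 sample compared to date of Vacc1 not in window". Crit25 covers a missed booster: "no Vacc 3 (within 180 days post Day 184), then exclude samples where the sample date>Day184+30". The Day 71 sample is different, because Crit34 checks it against the second vaccination: "Day 71 sample compared to date of Vacc2 not in window".

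**Analyses.** SAP 5.8.1 runs immunogenicity on the PPI and also on the FAS. SAP 5.8.1.4.1 plans fold increases from pre-dose 3 for the time points after the booster.

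**The concern.** Crit22 and Crit23 are listed under major deviations with an impact on immunogenicity. In Groups 1–3 the injection concerned carries no antigen, and the SAP itself does not use its date to time either the booster or the Day 184 sample. A participant whose Day 184 draw, booster and post-booster draws all meet their own windows can still lose all of those results from the PPI because a saline injection was early, late or missed. The secondary booster objective in Groups 1–3 is analysed on that set.

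A second gap affects the same objective. The window for accepting a booster is much wider than the window for accepting the draw taken just before it. A late booster can therefore leave post-booster titres in the PPI without the value against which the planned fold increase is measured.

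**Working it through.** **1. Second-vaccination window.** SAP: 57 − 8 = Day 49 to 57 + 8 = Day 65. Protocol schedule of activities (57 −3/+7): Day 54 to Day 64. A placebo given inside the protocol window never triggers Crit22; the first late trigger is Day 66.

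**2. Off-window placebo.** Humoral draws in Groups 1–3 (protocol 1.3.1) are on Days 1, 29, 57, 71, 184, 198 and 366, seven in all. With the booster on Day 184 and the criteria applied as written:

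| Vacc 2 given on Day | Days 1, 29 | Day 57 draw | Day 71 | Days 184, 198, 366 |
|---|---|---|---|---|
| 57, 64 or 65 | kept | kept | kept | kept |
| 48, 66 or 80 | kept | out (Crit22, and its own window) | out (Crit22) | out (Crit22) |

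In the second row the Day 184 sample passes its own check (184 ± 30 = Day 154–214 from Vaccination 1), and the booster passes Crit24 (184 − 30 = Day 154 to 184 + 180 = Day 364). The loss at issue is 3 of 7 draws. Day 71 is set aside because it is timed from the second vaccination.

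**3. Missed placebo.** The Crit23 cut-off is 57 + 8 = Day 65; the Crit25 cut-off is 184 + 30 = Day 214. A Day 184 sample without a booster passes Crit25 but fails Crit23. Under protocol 7.1, participants withheld from vaccination receive no further dose but stay in immunogenicity follow-up, so the usual loss is one draw (Day 184). Days 198 and 366 are lost through Crit23 only if the placebo was skipped and the booster still given.

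**4. Lifting the rules in Groups 1–3.** With Vacc 2 on Day 66 and Crit22 not applied, Days 184, 198 and 366 return. The Day 57 draw stays out through its own window.

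**5. Pre-booster draw.** The protocol's latest booster day is 184 + 30 = Day 214. Crit24 accepts boosters to Day 364. Crit35 with the ± 30 day rule accepts the draw only to Day 214. The gap is Days 215–364. For example, with a booster on Day 240 and the draw taken that day as scheduled, the booster passes (240 ≤ 364) and post-booster samples stay. The draw fails (240 > 214), so the fold increase from pre-dose 3 cannot be computed. There is no gap for boosters inside the protocol window.

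**6. Precision.** The documents give no off-window rate. Assume 5% or 10% of 50 per group: 5% is 2.5 participants, leaving 47 or 48; 10% leaves 45. The half-width ratio on the log scale, at equal SD, is [t(0.975, n−1)/√n] ÷ [t(0.975, 49)/√50]:

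- n = 48: 1.022
- n = 47: 1.033
- n = 45: 1.057

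The interval widens by about 2–6%.

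**The case against.** A PPI that treats every group alike is a legitimate choice in an observer-blind trial that compares groups. Protocol 9.3 excludes samples after missed vaccinations without distinguishing placebo. Crit22 also has a purpose in Groups 1–3: an off-window placebo shifts the Day 71 draw relative to the only active dose. The SAP window is wider than the protocol's, and delays from a study pause are not excluded by default (SAP 4, footnote a). All of this stands, and it is why the PPI should remain the main analysis.

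A reader might infer that no planned analysis shows the affected samples at all. That is not so: the FAS analyses retain them and show infected participants as a subgroup. But the FAS also restores off-window and post-infection samples, and SAP 5.4.3 promises only selected FAS analyses. The one labelled sensitivity analysis (SAP 5.6) starts from the PPI and censors further.

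SAP 5.1.4 allows windows to be redefined if too many samples are lost, but only before unblinding. The sponsor is unblinded at the primary analysis (SAP 5.9), and SAP 2 already reports its results.

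A reader might also see two conflicting rules for the pre-booster draw, since 5.1.4 has a pre-vaccination bullet. The text does not support that. The bullets are cumulative exclusions, and meeting one does not protect a sample that fails another. The rule is clear; its result is the problem.

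**Conclusion.** The point holds and is minor. In Groups 1–3 an off-window saline injection removes 3 of 7 scheduled humoral draws per affected participant from the PPI. A missed one removes the Day 184 draw, or three draws if the booster was still given. No planned analysis isolates that exclusion. For boosters on Days 215–364, Crit24 and Crit35 together keep the response and delete its reference.

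The 2–6% widening rests on an assumed 5–10% affected and on unchanged SD. The true loss may be smaller, because some reasons for withholding the second dose, such as an outside COVID-19 vaccine, remove later samples anyway. The endpoint is secondary and descriptive, with no hypothesis test. The documents do not support reading this as an error in the main analysis set or as a threat to a primary result: Day 29 is untouched and Day 71 is properly tied to the second vaccination.

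**What to change.** 1. Keep the prespecified PPI as the main analysis. Add one PPI sensitivity analysis for Groups 1–3 in which Crit22, Crit23 and the matching 5.1.4 bullet do not remove Day 184 and post-booster samples, with all other criteria unchanged. SAP version 5.0 added a PPI sensitivity analysis for N-ELISA rises in the same way. Record this one in SAP 6.2, now marked not applicable, as specified after sponsor unblinding and as a departure from protocol 9.3.
2. In Crit35 and 5.1.4, state that when the booster meets Crit24, the sample drawn before the booster on the booster day is kept as the pre-dose-3 reference for the fold increase. It is not reported as a Day 184 persistence value if it falls outside Day 154–214.

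The cost is a few lines in SAP 5.1.4 and 6.3, one entry in 6.2, and one extra set of Groups 1–3 tables. There are two drawbacks. The analysis is specified after unblinding, so it can only be supplementary. Within it, the second-vaccination criteria differ from those in Groups 4–6, so comparisons with the 6-month samples of those groups need that caveat.

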5.1.5. Pooling Algorithm for Analysis Centers

Data will be pooled across the different centers.

5.1.6. Analyses by Groups and Pooled Across Groups

In Part 1, summary outputs will be produced with pooled study groups that received the same dose up to D57 in addition to the analyses planned for each study group separately, unless specifically indicated otherwise. Immunogenicity analyses will be carried out by SARS-CoV-2 serostatus at baseline (in participants with a baseline result by central N- and S- serology testing, in PPI or FAS) and 'overall' (all participants, in PPI or FAS).

5.2. Participant Dispositions

Screened participants and reason for screen failures will be summarized overall.

The number of participants in the following disposition categories will be summarized by study group (where applicable) and overall:

- Participants screened
- Participants randomized
- Participants in FAS
- Participants in PPI
- Participants who completed the study
- Participants who discontinued vaccination
- Participants who terminated study prematurely

- Reasons for termination of study
- Participants who discontinued study

Listings of participants will be provided for the following categories:

- Participants vaccinated and not randomized
- Participants randomized and not vaccinated
- Participants who discontinued study
- Participants who discontinued vaccination
- Participants who were unblinded during the study period.

Participants with major protocol deviations will be identified prior to database lock and will be summarized by category. Details are available in Section [6.5](#).

5.3. Extent of Exposure

The number and percentage of participants who receive study vaccination, as well as the number of days between the 2nd and 1st vaccination, the number of days between the Day 29 sample and the 1st vaccination, and the number of days between the Day 71 sample and the 2nd vaccination will be summarized by vaccination schedule. The number and percentage of participants by visit (Day 1, Day 29, Day 57, Day 71, etc) will similarly be summarized.

Study vaccination compliance will be summarized descriptively by vaccination schedule. Details are available in Section [6.7](#).

5.4. Primary Endpoints Analysis

5.4.1. Definition of Endpoint(s)

Safety and Reactogenicity Endpoints

Section [5.7.1](#) provides AE definitions associated with primary and secondary safety and reactogenicity endpoints.

The primary endpoints to assess the safety and reactogenicity are:

- Solicited local and systemic AEs for 7 days post-dose 1 and 2.
- Unsolicited AEs for 28 days post-dose 1 and 2.
- MAAEs from the first vaccination until 6 months post-last dose.
- SAEs, AESIs (TTS and MIS-C) and MAAEs leading to discontinuation from the first vaccination until the end of the study.

Humoral Immune Response Endpoints

S-ELISA (or equivalent assay, e.g. MSD) or VNA will be used as primary humoral immune response endpoint to assess the serological response to vaccination in Part 1:

- Serological response to vaccination as measured by S-ELISA (ELISA Units/mL [EU/mL]) or equivalent assay, or VNA titers at 28 days post-dose 1, and 14 days post-dose 2.

For S-ELISA or equivalent assay (e.g. MSD), wild type, and pseudovirion VNA, a sample is defined as positive if its value is strictly greater than the LLOQ (>LLOQ).

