a Not more than 70% of males or females should be randomized in each age group.

b All participants must be seronegative for SARS CoV 2 antibodies at baseline (by finger prick test).

c Approximately 30% of participants should be between 16 to 17 years age and approximately 70% should be between 12 to 15 years of age.

d Participants in Groups 1-3 will be given a booster vaccination as of 6 months after the last vaccination with active vaccine (Vaccination 1) and the booster dose level for these participants will be 2.5 × 10¹⁰ vp per 0.5 mL.

Study Duration

The study duration from screening until the last follow-up visit will be, excluding the 28-day screening phase, approximately 8 months (Groups 4-6) to 12 months (Groups 1-3) provided the intervals in the SoA are respected, consisting of:

- Groups 1-3: ~12-month study duration comprising a 6-month study period including vaccination with 1 active dose and a placebo vaccination (56-day interval), followed by a booster vaccination at 6 months and follow-up (safety and immunogenicity) until at least 6 months after booster vaccination.
- Groups 4-6: ~8-month study duration comprising 2 active doses (56-day interval) and follow-up (safety and immunogenicity) until at least 6 months after second vaccination.

If a participant is unable to complete the study, but has not withdrawn consent, an early exit visit will be conducted. The end of study is considered as the last visit for the last participant in the study.

Study Procedures

For each group, safety will be assessed by collection of solicited local (at injection site) and systemic AEs, unsolicited AEs, MAAEs, SAEs, and AESIs. Other safety assessments include vital signs measurements (heart rate, preferably supine systolic and diastolic blood pressure, respiratory rate, and body temperature) and physical examinations at the time points indicated in Section 1.3, Schedule of Activities.

After each vaccination, participants will remain under observation at the study site for at least 30 minutes (or longer if required by institutional/local practice) for presence of any acute reactions and solicited events. Any solicited local or systemic AEs, unsolicited AEs, SAEs, AESIs, concomitant medications, and vital signs will be documented by study-site personnel following this observation period, and participants will be allowed to leave the study site after it is

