1.1. Objectives and Endpoints

Part 1: Objectives and Endpoints

Objectives	Endpoints
Primary	

 To assess the safety and reactogenicity of Ad26.COV2.S administered intramuscularly as a 1-dose regimen (at 2.5×10^{10} vp per 0.25 mL, 1.25×10^{10} vp, and 0.625×10^{10} vp dose level) or as a 2-dose (56-day interval) regimen (2.5×10^{10} vp per 0.5 mL, 1.25×10^{10} vp, and 0.625×10^{10} vp dose levels) in adolescents. 	
 Solicited local and systemic adverse events (AEs) for 7 days post-dose 1 and 2. Unsolicited AEs for 28 days post-dose 1 and 2. Medically-attended adverse events (MAAEs) from the first vaccination until 6 months post-dose 1 or post-dose 2. MAAEs leading to discontinuation will be collected during the entire study. Serious adverse events (SAEs) from the first vaccination until the end of the study. Adverse events of special interest (AESIs) from first vaccination until end of the study (incl. multisystem inflammatory syndrome in children [MIS-C]).

 To assess the humoral immune response of Ad26.COV2.S administered IM as a 1-dose regimen (at 2.5×10^{10} vp per 0.25 mL, 1.25×10^{10} vp, and 0.625×10^{10} vp dose level) or as a 2-dose (56-day interval) regimen (2.5×10^{10} vp per 0.5 mL, 1.25×10^{10} vp, and 0.625×10^{10} vp dose levels) in adolescents. 	
 Serological response to vaccination as measured by spike-enzyme-linked immunosorbent assay (S-ELISA) (ELISA; Units/mL [EU/mL]) or equivalent assay, or virus neutralization assay (VNA) titers at 28 days post-dose 1 and 14 days post-dose 2.

Secondary and Exploratory Objectives and Endpoints for Part 1

Secondary	

 To assess the humoral immune response to 3 dose levels of Ad26.COV2.S (2.5×10^{10} vp, 1.25×10^{10} vp or 0.625×10^{10} vp) and regimens in all study groups at all blood collection timepoints. 	
 Serological response to vaccination measured by binding antibody titers to SARS-CoV-2 or individual SARS-CoV-2 proteins (e.g, S protein) as measured by ELISA (or equivalent assay), and/or Serological response to vaccination measured by neutralizing antibody titers to SARS-CoV-2 (VNA).

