
 To assess the safety and reactogenicity of Ad26.COV2.S administered IM as a booster in adolescent participants (Groups 1-3). 	
 Solicited local and systemic AEs for 7 days post-booster. Unsolicited AEs for 28 days post-booster. MAAEs from the booster until 6 months post-vaccination.

 To evaluate the humoral immune response in adolescent participants who receive a booster dose during the study, pre-boost and at selected time points post booster vaccination (Groups 1-3). 	
 Serological response to vaccination measured by binding (S-ELISA and/or equivalent assay) and/or neutralizing (VNA) antibody titers

Exploratory	

 To examine the immune response in vaccinated adolescents after SARS-CoV-2 infection. 	
 Confirmation of SARS-CoV-2 infection by molecular testing.⁽¹⁾ SARS-CoV-2 neutralizing titers in serum measured by a VNA.⁽¹⁾ SARS-CoV-2-binding antibodies measured by ELISA (or equivalent assay): Analysis of antibodies binding to the SARS-CoV-2 S and/or N protein.⁽¹⁾ Analysis of gene expression by ribonucleic acid (RNA) transcript profiling in adolescents.⁽¹⁾

 To assess the correlation between the binding antibodies (S-ELISA) and neutralizing antibody (VNA) titers to SARS-CoV-2 at selected timepoints. 	
 Correlation between ELISA (S-ELISA; EU/mL, or equivalent assay) and VNA (wtVNA⁽¹⁾ and/or psVNA) titers at selected timepoints.

 To assess the occurrence of symptomatic molecularly confirmed COVID-19 and severity of COVID-19 signs and symptoms in adolescents. 	
 The number of adolescents with molecularly confirmed COVID-19.⁽¹⁾ Presence and severity of COVID-19 signs and symptoms as measured by the Symptoms of Infection with Coronavirus-19 (SIC).

 To assess for the occurrence of asymptomatic SARS-CoV-2 infection. For Asymptomatic case definition: See CTP Section 10.9.3 	
 Serologic conversion between baseline (Day 1; pre-vaccination) and selected timepoints post-vaccination using an ELISA and/or SARS-CoV-2 immunoglobulin assay that is dependent on the SARS-CoV-2 N protein The number of asymptomatic participants with a SARS-CoV-2 positive molecular test.

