5.1.3. Phase Definitions

The phases in the Part 1 will be constructed as described in [Table 3](#).

Table 3: Phase Definitions

Phase	Phase #	Period	Period #	Interval	
				From	To
Screening	1			Date and time of signing the IC form	One second prior to start of post dose 1 period
Post-dose	2	Post-dose 1	1	Date and time of first vaccination	
Minimum of:
 
 a) 23:59:59 at the date of last contact (for early discontinuation) b) 23:59:59 at the date of data base cut-off date in case of interim analysis c) 23:59:59 on 28 days after the first vaccination (23:59:59 of day of vaccination + 28 days) d) One second prior to date and time of second vaccination e) One second prior to date and time of Booster Vaccination f) One second before date and time of another viral vaccination outside the study
Follow-up 1	3			One second after Post-dose 1 period end	
Minimum of:
 
 a) 23:59:59 at the date of last contact (for early discontinuation) b) 23:59:59 at the date of data base cut-off date in case of interim analysis c) One second prior to 6 months after first vaccination (vaccination date + 6 mths) d) One second prior to date and time of second vaccination e) One second prior to date and time of Booster Vaccination f) One second before date and time of another viral vaccination outside the study
Post-dose	2	Post-dose 2	2	Date and time of second vaccination	
Minimum of:
 
 a) 23:59:59 at the date of last contact (for early discontinuation) b) 23:59:59 at the date of data base cut-off date in case of interim analysis c) 23:59:59 on 28 days after the second vaccination (23:59:59 of day of vaccination + 28 days) d) One second prior to date and time of Booster Vaccination e) One second before date and time of another viral vaccination outside the study

Table 3: Phase Definitions

Phase	Phase #	Period	Period #	Interval	
				From	To
Follow-up 2	4			One second after Post-dose 2 period end	
Minimum of:
 
 a) 23:59:59 at the date of last contact (for early discontinuation) b) 23:59:59 at the date of data base cut-off date in case of interim analysis c) One second prior to 6 months after second vaccination (vaccination date + 6 mths) d) One second prior to date and time of Booster Vaccination e) One second before date and time of another viral vaccination outside the study

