5.1.3.1. Other Follow-up Visits

The following other time intervals will be derived for safety data summary as shown in [Table 4](#).

Table 4: Other Time Intervals

Time Intervals	From	To
Up to Day 85 (only for the primary analysis)	Date and time of first vaccination	Maximum of: a) Post-dose 1 end date b) Follow-up 1 end date c) Post-dose 2 end date
Primary Vaccination Period	Date and time of first vaccination	Maximum of: a) Post-dose 1 end date b) Follow-up 1 end date c) Post-dose 2 end date d) Follow-up 2 end date e) Long term follow-up
Booster Vaccination Period	Date and time of Booster Vaccination	Maximum of: a) Post-dose 3 end date b) Booster follow-up 1 end date c) Booster long term follow-up
Entire Study	Date and time of first vaccination	Maximum of: a) Primary Vaccination Period end date b) Booster Vaccination Period end date

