5.7.1. Adverse Events

5.7.1.1. Definitions

Solicited AEs are used to assess the reactogenicity of the study vaccine and are predefined local events (pain/tenderness, erythema, and swelling at the injection site) and systemic events (fatigue, headache, nausea, and myalgia, fever) for which the participant or parent(s)/caregiver(s) is specifically questioned, and which are noted by participants or parent(s)/caregiver(s) in their reactogenicity diary. Unsolicited AEs are all AEs for which the participant or parent(s)/caregiver(s) is not specifically questioned.

MAAEs are defined as AEs with medically-attended visits including hospital, emergency room, urgent care clinic, or other visits to or from medical personnel for any reason. Routine study visits will not be considered medically-attended visits. New onset of chronic diseases will be collected as part of the MAAEs. MAAEs are to be reported for all participants from the first vaccination until 6 months after each vaccination, except for MAAEs leading to study discontinuation which are to be reported during the entire study.

Solicited AEs shown in the tables are extracted from the investigator assessment pages (CE) of the CRF. Solicited administration site symptoms will by definition be considered as related to the study vaccine.

The following adverse events of special interest (AESI) will be collected in this study:

- Thrombosis with Thrombocytopenia Syndrome (TTS), defined as:
 - Thrombotic events: suspected deep vessel venous or arterial thrombotic events as detailed in CTP Section 10.14 and in Section [6.10](#)
 - Thrombocytopenia, defined as platelet count below 150,000/ μ L.
- Multisystem Inflammatory Syndrome in Children (MIS-C), defined as:
 - An individual aged <21 years presenting with fever^a, laboratory evidence of inflammation^b, and evidence of clinically severe illness requiring hospitalization, with multisystem (≥ 2)

^a Fever $>38.0^{\circ}\text{C}$ for ≥ 24 hours, or report of subjective fever lasting ≥ 24 hours.

^b Including, but not limited to, one or more of the following: an elevated C-reactive protein (CRP), erythrocyte sedimentation rate (ESR), fibrinogen, procalcitonin, D-dimer, ferritin, lactic acid dehydrogenase (LDH), or interleukin 6 (IL-6), elevated neutrophils, reduced lymphocytes, and low albumin.

- organ involvement (cardiac, renal, respiratory, hematologic, gastrointestinal, dermatologic, or neurological); AND
- No alternative plausible diagnoses; AND

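### At the final analysis, crude MAAE, SAE and AESI percentages are summarised by group over intervals of unequal planned length, so equal risk would show as a regimen difference

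*SAP*

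**What the plan says.** The primary safety endpoints extend well beyond the early post-dose periods. SAP 5.4.1 gives the MAAE window as "MAAEs from the first vaccination until 6 months post-last dose" and adds "SAEs, AESIs (TTS and MIS-C) and MAAEs leading to discontinuation from the first vaccination until the end of the study". SAP 1.1 words the MAAE window differently: "Medically-attended adverse events (MAAEs) from the first vaccination until 6 months post-dose 1 or post-dose 2". SAP 5.7.1.1 gives the collection rule: "MAAEs are to be reported for all participants from the first vaccination until 6 months after each vaccination". For Groups 1-3, SAP 1.1 also lists a separate secondary endpoint, "MAAEs from the booster until 6 months post-vaccination".

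SAP 5.1.3 (Table 3) closes Follow-up 2 at the earliest of several dates, including six months after the second vaccination and the moment before the booster. Long term follow-up also closes at the booster. SAP 5.1.3.1 introduces the cumulative intervals with "The following other time intervals will be derived for safety data summary as shown in" Table 4. These are an interval up to Day 85 (for the primary analysis only), the Primary Vaccination Period, the Booster Vaccination Period and Entire Study.

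Only Groups 1-3 receive a booster, planned for Day 184. Protocol 4.1 states the resulting study duration as "approximately 8 months (Groups 4-6) to 12 months (Groups 1-3) provided the intervals in the SoA are respected".

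The statistic in SAP 5.7.1.3 is the number and percentage of participants with at least one event. Protocol 9.4.2 says the same, by vaccine group. SAP 5.7.1.5 counts a participant with no reported event as event-free. SAP 5.3 summarises vaccinations, intervals between vaccinations and samples, and attendance by visit, but not follow-up time.

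**The concern.** A crude percentage with at least one event rises with time observed. If two regimens are shown in adjacent columns over intervals of different length, the longer-observed one will tend to show more events even when the underlying risk is the same.

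Here the imbalance also changes sign. The 2-dose groups are observed longer in the Primary Vaccination Period, and the 1-dose groups are observed longer in Entire Study. Two tables in one report could therefore point in opposite directions with no real difference behind either.

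The MAAE wording adds to this. In Groups 1-3, six months after the last dose could mean about Day 184 (last active dose before the booster), about Day 240 (counting the Day 57 placebo) or about Day 366 (counting the booster).

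**Working it through.** **Inputs.** The schedules in Protocol 1.3.1 and 1.3.2 give dose 2 on Day 57, the booster on Day 184 (window +30 days), and the last visit on Day 366 (Groups 1-3) or Day 240 (Groups 4-6). The closing rules come from SAP Tables 3 and 4. Six months after Day 57 is 57 + 183 = Day 240.

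**The plan's own durations.** Elapsed days divided by 30.4375: 239/30.4375 = 7.9 months and 365/30.4375 = 12.0 months. These reproduce the stated 8 and 12 months.

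**Planned interval lengths.**

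| Interval | Groups 1-3 | Groups 4-6 | Ratio, longer to shorter |
|---|---|---|---|
| Up to Day 85 | 84 days elapsed | 84 days elapsed | 1.00 |
| Follow-up 2 | Days 86-183 = 98 days | Days 86-239 = 154 days | 154/98 = 1.57 |
| Primary Vaccination Period | to Day 184, 183 days elapsed | to Day 240, 239 days elapsed | 239/183 = 1.31 (240/184 = 1.30) |
| Entire Study | to Day 366, 365 days elapsed | to Day 240, 239 days elapsed | 365/239 = 1.53 |

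A booster at the end of its visit window (Day 214) reduces the Primary Vaccination Period ratio to 239/213 = 1.12. Post-booster visits are timed from the actual booster, so the same delay moves the last visit to 214 + 182 = Day 396 and raises the Entire Study ratio to 395/239 = 1.65.

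**Effect on the percentages.** The documents give no MAAE, SAE or AESI rate. Assume the same constant hazard in every group, with cumulative risk p0 by Day 184. The risk after t elapsed days is then p(t) = 1 - (1 - p0)^(t/183).

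| p0 (assumed) | Day 184 | Day 240 | Day 366 | Primary Vaccination Period, Groups 4-6 higher by | Entire Study, Groups 1-3 higher by |
|---|---|---|---|---|---|
| 1% | 1.0% | 1.3% | 2.0% | 0.3 points | 0.7 points |
| 5% | 5.0% | 6.5% | 9.7% | 1.5 points | 3.2 points |
| 10% | 10.0% | 12.9% | 19.0% | 2.9 points | 6.1 points |
| 30% | 30.0% | 37.2% | 50.9% | 7.2 points | 13.7 points |

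At 10%, Follow-up 2 alone would show 5.5% v 8.5%, so presenting results by phase does not remove the problem in that phase.

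**Scale against sampling error.** With 150 participants per regimen, the 90% half-width of a difference is 1.645 × sqrt[p1(1-p1)/150 + p2(1-p2)/150]. At p0 = 10% this is 6.0 points for the Primary Vaccination Period and 6.9 points for Entire Study, against artefacts of 2.9 and 6.1 points.

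**With a common interval.** Cut at Day 184, both regimens have 183 days elapsed and the artefact is zero under the same assumption.

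**The case against.** The strongest reply is that the analysis that matters is protected. Table 4 has a common interval up to Day 85. The primary analysis, on data to 28 days post-dose 2, is where SAP 5.9 says the dose level is selected. Post-dose 1, Follow-up 1 and Post-dose 2 also have equal planned lengths in all groups. That stands: a reader might infer that dose selection is biased, and the documents do not support it. The Day 85 row does not, however, apply at the final analysis, and it cannot cover endpoints that run to six months or to the end of the study.

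Second, safety is summarised, not tested. The Go/No-Go guideline in SAP 5.9.1 concerns Grade 3 local and systemic events against young adults, and is not to be assessed in this study. That also stands. The harm is to how descriptive tables are read.

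Third, a reader might take 366 v 240 days as the primary MAAE contrast. It is not: Table 3 assigns post-booster time to booster phases, and post-booster MAAEs are a secondary endpoint. The primary MAAE contrast is about 184 v 240 days. The longer contrast applies to SAEs, AESIs and the Entire Study tables. Nor is an Entire Study difference purely a matter of time observed, because Groups 1-3 have by then received a further active dose.

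Fourth, SAP 5.7.1.3 does not say which Table 4 interval each AE table uses; layouts are left to a separate specification document. The exact set of affected tables is therefore an inference, although Table 4 states that its intervals are for summarising safety data.

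Finally, the unequal follow-up is deliberate and disclosed. That justifies the design, but not unadjusted percentages shown next to each other.

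**Conclusion.** The point holds for the final-analysis safety summaries and no further. The planned lengths are unequal by ratios of about 1.3 (1.12 with a booster on Day 214) for the Primary Vaccination Period, 1.57 for Follow-up 2 and 1.53 for Entire Study. The plan specifies neither person-time rates nor a follow-up summary.

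At an assumed 10% risk by Day 184 the expected artefact is 2.9 points against the 2-dose groups, then 6.1 points against the 1-dose groups. For rare SAEs and AESIs at about 1% it is under one point. Both shifts at 10% lie within sampling error for 150 per regimen, so the tables will not necessarily look different. The bias is in expectation, and it misleads on direction.

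The sizes rest on an equal, constant hazard. If events cluster soon after vaccination, the Primary Vaccination Period artefact would be smaller. The inconsistent MAAE wording needs reconciling whatever the size.

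**What to change.** 1. Add a row to SAP Table 4 for all six groups: first vaccination to Day 184, or to the booster if earlier. Use it for every side-by-side MAAE, SAE and AESI table at the final analysis.
2. For Follow-up 2, Primary Vaccination Period and Entire Study, report events per person-time beside the percentages, with a summary of follow-up time by group. Person-time rates remove the artefact only if the hazard is roughly constant, so the common interval should carry the comparison.
3. Reconcile the MAAE window across SAP 1.1, SAP 5.4.1 and Table 3. State that in Groups 1-3 the primary window ends at the booster and that later events count only under the secondary booster endpoint.

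The cost is SAP wording and a few extra table columns, with no new data and no change to conduct. The one downside is that events in Groups 4-6 after Day 184 leave the side-by-side table and appear in a separate one.
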